Compliance reports which include telephone screening forms for eligibility, radiographs, medication amenability and safety logs will be reviewed by the Principal Investigator on a weekly basis. Reports containing the proportion of subjects completing the intervention or prematurely terminating participation will be generated monthly.

Adverse event information will be collected at each visit and during all contacts with subjects. If an adverse event is reported to study staff, data including the type of event, onset/end dates, duration, and outcome will be collected and reported to the Principal Investigator. All adverse event information will be assessed by the Principal Investigator for severity, seriousness, and relationship to Zilretta, per the definitions below.

The Investigator is required to follow SAEs until resolution or withdrawal of consent. Resolution is defined as:

- A return to baseline for a pre-existing condition; or
- Resolved with or without residual effects; or
- The Investigator does not expect any further improvement or worsening of the event.

Reporting Serious Adverse Events:

An event that is serious must be recorded on the AE worksheet and requires expeditious handling to comply with regulatory requirements. Any adverse event classified as “serious” by the Investigator must be reported to the IRB within 24 hours of becoming aware of its occurrence. All serious adverse events in patients treated with Zilretta must also be reported to Flexion within 3 calendar days. The Investigator should attempt to collect as much information about the adverse event as needed to get a complete medical understanding and forward that information to Flexion as it becomes available.

All serious adverse events which are considered causally related to Zilretta (see definitions below) must be assessed for whether it is expected per the USPI. An unexpected event means that it is not described within the reference safety information (the Zilretta USPI) as associated with Zilretta. If an event is assessed as serious, related to Zilretta, and unexpected, it must be reported to the FDA according to 21CFR314.80

Safety Definitions:

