- Severe: the AE significantly limits the patient's ability to perform routine activities despite symptomatic therapy.

Causal Relationship: A medically-qualified Investigator must assess the relationship of any AE (including SAEs) to the use of the investigational product, as related or not related, based on clinical judgment and using all available information, and may include consideration of possible alternative causes of the AE, including the disease under treatment, pre-existing conditions, concomitant use of other drugs, and presence of environmental or genetic factors, the temporal association between drug exposure and onset of the AE, and whether the manifestations of the AE are consistent with known actions or toxicity of the investigational product. The causal relationship between the study medication and the AE will be assessed using one of the following categories:

- **Not Related:** An AE is not associated with study medication if:
 - Temporal relationship is lacking (e.g., the event did not occur within a reasonable time frame following administration of the study medication); or
 - Other causative factors more likely explain the event (e.g., a pre-existing condition, other concomitant treatments).
- **Related:** An AE is attributed to the study medication if:
 - There is a positive temporal relationship (e.g., the event occurred within a reasonable time frame following administration of study medication); and
 - The AE is more likely explained by the investigational product than by another cause (i.e., the AE shows a pattern consistent with previous knowledge of the investigational product or the class of the investigational product).

Data and Safety Monitoring Plan

The data will be reviewed by the study team and the Principal Investigator. The reviewed data include eligibility, data reconciliation and safety logs. There will also be reports containing the proportion of subjects completing the intervention or prematurely terminating participation . This will be done on a monthly basis.

III. Subject Participation

A. Recruitment:

Potential study subjects will be recruited from the clinics of the principal investigator and referring physicians, and using local advertising. Any study-related advertisements will be approved by the governing IRB prior to use. Subjects will be recruited based upon inclusion and exclusion criteria detailed above. Subjects will be compensated for their time and effort at follow-up visits.

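### The causality definitions leave a serious event that is new to both product and class without a category, so the protocol's FDA report may not be triggered

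*Combined protocol and SAP*

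**What the plan says.** The section on adverse event collection says that the Principal Investigator assesses relationship to Zilretta by the definitions that follow it. Under Causal Relationship, the assessor classifies each event "as related or not related, based on clinical judgment and using all available information". Agreement with known toxicity appears there as one of several things that may be weighed. The protocol then requires one of two categories.

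- **Not Related** applies on either of two grounds: "Temporal relationship is lacking", or "Other causative factors more likely explain the event".
- **Related** needs two conditions together. The first is "There is a positive temporal relationship". The second is worded "The AE is more likely explained by the investigational product than by another cause (i.e., the AE shows a pattern consistent with previous knowledge". Through *i.e.*, the text thus equates being the likelier cause with having a precedent, either for Zilretta or for its class.

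Under Reporting Serious Adverse Events, the FDA rule is "If an event is assessed as serious, related to Zilretta, and unexpected, it must be reported to the FDA according to 21CFR314.80". Expectedness is defined just before it: "An unexpected event means that it is not described within the reference safety information (the Zilretta USPI) as associated with Zilretta".

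The same subsection sends every SAE to the IRB within 24 hours of awareness and to the manufacturer within 3 calendar days. Neither duty depends on causality or expectedness.

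**The concern.** Prior knowledge is used twice, in opposite directions. Read literally, an event needs precedent to count as Related, and it then needs to be missing from the USPI to count as unexpected. The FDA report requires both. The kind of event for which an expectedness rule matters most, a serious reaction not seen before with the product or its class, is the one that the written Related definition does not admit.

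The study has one open-label arm, so no concurrent control rate could show that events had been misclassified. Individual causality judgments therefore carry more weight than they would in a controlled trial. The definitions also apply to every AE, not only to serious ones.

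**Working it through.** No figure in the plan bears on this point and no formula applies. The check sets the two causality categories against the FDA rule and goes through the kinds of serious event that can arise.

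Four features decide the outcome:
- whether the timing fits (both categories);
- whether the product, another cause or neither is the likelier explanation (both categories);
- whether the pattern has precedent for the product or class (Related only, through *i.e.*);
- whether the event is in the USPI (FDA rule only).

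| Case | Timing fits | Likelier cause | Precedent | In USPI | Category as written | FDA trigger as written |
|---|---|---|---|---|---|---|
| 1 | No | any | any | any | Not Related | No |
| 2 | Yes | Other cause | any | any | Not Related | No |
| 3 | Yes | Product | Yes | Yes | Related | No (expected) |
| 4 | Yes | Product | Yes, e.g. class only | No | Related | Yes |
| 5 | Yes | Product | None | No | **None** | **Undetermined** |
| 6 | Yes | Equal | any | either | **None** | No if in USPI, otherwise **undetermined** |

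**Case 5.** The event fails the second Related condition because it has no precedent. It fails both Not Related grounds because the timing fits and no other cause is likelier; unfamiliarity is not a ground for Not Related. It is also always unexpected, since an event with no precedent for the product cannot be described in the USPI as associated with it. Whether it reaches the FDA step therefore depends entirely on which category the assessor picks, and the text gives no rule for that.

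**Case 6.** Related needs the product to be likelier, and Not Related needs another cause to be likelier. A tie satisfies neither. This gap does not depend on how *i.e.* is read.

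**Internal conflict.** The introductory text to Causal Relationship makes agreement with known toxicity optional. The Related definition makes agreement with product or class knowledge a condition. Both cannot govern the same judgment.

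**After the change under fix.** Cases 1 to 4 keep their outcomes. Case 5 becomes Related and triggers the report. Case 6 becomes Related and triggers the report when the event is not in the USPI.

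**The case against.** The strongest reply is that the introductory text governs. Causality is a clinical judgment on all the information, the operative test is which cause is likelier, and the parenthesis only illustrates that test. The other parentheses in the two definitions use *e.g.*, so *i.e.* may be a slip. A sensible investigator would code a striking, otherwise unexplained event as Related. This shows that the FDA report is not ruled out. It does not remove the defect: assessment is to follow the written definitions, and the assessor reaches Related in case 5 only by setting part of one aside. If it is a slip, that is a reason to correct it. The reply also does nothing for case 6.

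The second reply is that no serious event is lost, because the IRB and manufacturer reports do not depend on causality. That stands, and it limits the problem to causality coding and the FDA step.

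A reader might infer more than the documents support:
- *A new serious reaction is coded Not Related and never reported to the FDA.* The text does not send it there. It meets neither Not Related ground, so that code is a possible outcome of a forced choice, not a stated rule.
- *The two rules cancel, so nothing can qualify.* Precedent may come from the class, whereas expectedness is judged on the Zilretta USPI alone. The physical risk section itself lists corticosteroid events that it says have not been reported with Zilretta. How many are absent from the USPI cannot be known, because the USPI is not among the documents.
- *Bilateral dosing makes the gap acute.* Each subject receives 2 × 32 mg = 64 mg, but effects of greater corticosteroid exposure would be consistent with the class and would meet the precedent condition.
- *The count of related AEs is biased downward.* The statistical section, in the text available, specifies no such count, so there is no defined quantity to be biased.

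**Conclusion.** The point holds in a limited form. On a literal reading, two of the six kinds of serious event have no causality category although one must be assigned: the event new to both product and class, and the event with equally likely causes. For the first, and for the second when it is absent from the USPI, whether the protocol's FDA trigger is met is left undetermined.

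The conclusion on the new event assumes that *i.e.* is read as a condition; the conclusion on ties does not. Two of six counts kinds of event, not their frequency, and the documents give no basis for estimating how often either would occur among 70 subjects. No endpoint, sample size, alpha level or power figure changes. This is an operative safety rule that is wrong as written and should be corrected, but it is not among the most serious faults a plan can have.

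**What to change.** Reconcile Causal Relationship with Reporting Serious Adverse Events in three steps:

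1. In the Related definition, delete the *i.e.* parenthesis, or make consistency with prior knowledge a supporting consideration only, for example by changing it to *e.g.* This also brings the definition into line with its introductory text.
2. Apply prior knowledge as a test at the expectedness step only.
3. State that an event meeting neither Not Related ground is coded Related. This settles both the unprecedented event and the tie.

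The cost is a few lines of protocol text and any matching causality key on the AE worksheet. The downside is that slightly more events will be coded Related.

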This will be an open-label study to determine the functional effects of IA injection of Zilretta into bilateral knees of 70 subjects with KL grade 2-4 symptomatic knee OA. Measurement of OARSI recommended physical performance measures¹⁰, patient-reported physical function, quality of life and pain at baseline, 6, 12 and 24 weeks will allow assessment of short and long-term effects, consistent with OARSI and OMERACT recommendations. Adverse events will be monitored.

Each subject will participate for up to 24 weeks following the intra-articular Zilretta injection. Enrollment is expected to take approximately 6 months. Total study duration is expected to require at least 12 months.

C. Sample size, statistical methods, and power calculation

In this open-label study, all subjects will receive a single IA Zilretta injection into each knee. Outcome measures will be collected at baseline, 6, 12 (primary) and 24 weeks post-treatment. A 24-week follow-up duration was selected to detect meaningful differences from standard of care (IA corticosteroids - TAcS) and long-term effects, while minimizing the variability that may occur further out from treatment. The overall type I error rate will be controlled with an alpha level of 0.0167 to account for three comparisons at the primary time point.

Based on the respective MDC₉₅ calculated from the standard error of the mean change for OARSI recommended physical performance¹, the effect size for this minimal detectable change is 0.392. To detect an effect size at least this large, with an adjusted alpha of 0.0167 and 80% power, a sample size of 60 would be required. To accommodate up to 14% dropout, we plan to recruit 70 subjects.

D. Subject Criteria (See Vulnerable Populations appendix, if applicable):

Enrollment will be comprised of 70 subjects age 30 and over with symptomatic bilateral knee OA. There will be no exclusions based on sex or ethnic group. Potential subjects will be identified through hospital records, referrals from physicians in the surrounding community, mass mailings, and advertisements posted in area clinics and businesses. Any study-related advertisements will be approved by the IRB prior to use. Subjects will be recruited based upon inclusion and exclusion criteria detailed below.

1. Inclusion Criteria

- Men and women age 30 years or older with symptomatic bilateral knee OA.

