- Women who report pregnancy or childbearing potential and not using acceptable contraceptive measures (oral contraceptive, long acting reversible contraceptive therapy) (due to the potential for change in body mass and distribution to alter knee symptoms over the period of follow-up).
- Presence of surgical hardware or other foreign body intended to treat arthritis or cartilage-related pathology in either knee.
- Arthroscopy or open surgery of either knee within 6 months of screening.
- Planned/anticipated surgery of either knee during the study period.
- Use of systemic immunosuppressant within 6 weeks of screening.
- Oral corticosteroids (investigational or marketed) within 2 weeks of screening.
- IA corticosteroid (investigational or marketed) in either knee within 3 months of screening.
- IV or IM corticosteroid (investigational or marketed) within 3 months of screening.
- Any other IA drug/biologic use within 6 months of screening or 5 half-lives (whichever is longer) (e.g., hyaluronic acid, platelet-rich plasma (PRP) injection, stem cells, prolotherapy and amniotic fluid injection).
- Any documented clinically significant degree of cognitive impairment or other condition, finding, or psychiatric illness at screening which, in the opinion of the investigator, could compromise subject safety.
- Any condition other than OA of the knee which, in the opinion of the investigator, affects the ability to ambulate to a sufficient degree to interfere with the assessment of the safety and treatment effects of the study injection.
- Participated in any investigational drug or device trial within 30 days prior to screening or concurrent participation in another research study that could complicate interpretation of the study findings.

3. Withdrawal/Termination criteria:

Subjects may discontinue the study at any time. The investigator may discontinue a subject at any time for subject safety or noncompliance. Subjects who are discontinued for safety will be referred to their primary care physician for follow-up.

The Investigator/Coordinator will complete a study exit form in the CRF for any subject who prematurely discontinues from the study. If discontinuation was the result of an AE, the AE also will be recorded in the CRF.

4. Allowable Medications/Nonpharmacological Therapies

The following medications and nonpharmacological therapies may be taken or used throughout the study:

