Zilretta (triamcinolone acetonide extended-release injectable suspension) is indicated as an intra-articular injection for the management of pain due to knee OA. To prepare the injectate, we will dilute 32 mg Zilretta in a 5 ml diluent for each knee, per manufacturer instructions. After application of sterile chlorhexidine and topical lidocaine (optional) for skin anesthesia, we will locate the superior recess of each knee joint, aspirate excess joint fluid and then inject the 5ml injectate into each knee joint capsule (bilateral injections).

Primary Outcome

OARSI recommended physical performance measures

OARSI (Osteoarthritis Research Society International) recommended physical performance measures¹ are a consensus-derived set that test physical function, which is complementary to patient-reported measures for

use in people diagnosed with knee osteoarthritis or following knee replacement. They are recommended for use prospectively as outcome measures in research, and also in clinical practice to make treatment decisions based on the results¹¹.

1. 30-second chair standing test

The 30-second chair standing test evaluates the maximum number of repetitions that a subject can stand from a seated position in a 30 second period¹. From the sitting position, the subject will stand up completely up so hips and knees are fully extended, then completely back in the seated position. This will be repeated for 30 seconds and we will record the total number of chair stands (up and down equals one stand). The tester will stand close to the side of the chair for safety and also ensure that the subject comes to a full standing and sitting position during the test.

The study coordinator or designee will enter the data collected into the CRF after completion of the test.

2. 40m fast-paced walking test

The 40-meter fast-paced walking test is a test that is timed over 4 x 10m (33 ft) paths for a total of 40 m (132 ft)¹. We will mark out a 10 m (33 ft) walkway with bright colored tape at each end. A cone will be placed approximately 2 meters before the start mark and 2 meters beyond the finish mark of the 10m walkway. Enough space will be left to turn safely around at each end.

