A practice trial of 1-2 turns will be done before testing to help subjects to understand the procedure. We will begin timing subjects after giving the signal to start at the start line and stop the timer once the subject crosses back over the start line after completing the course. When the subject crosses the 10m mark, timing will be paused while the subject turns around the cone and then it will be resumed once they cross the 10m mark again. The same will be repeated for the following turns and timing will be stopped once the subject crosses the start line for the final time. The duration of one trial will be recorded to the nearest 100th of a second. Time of one test trial will be recorded and expressed as speed (m/s) by dividing distance (40m) by total time. Regular walking aid will be allowed and its use will be recorded.

For subjects in whom safety is of concern, the tester will follow slightly behind and off to one side of the subject, while taking care not to pace or impede them. If there is no excess concern for safety, the tester will follow well to the side so as to view the crossing at the 10m walkway at both ends. The study coordinator or designee will enter the data into the CRF.

3. Stair negotiation

Stair negotiation is also a common activity limitation and rehabilitation goal in people with symptomatic knee OA. We will time the subjects ascending and descending a flight of 9 stairs as quickly as they can accomplish in a safe manner. We will conduct the nine-step stair test in the staircase adjoining our research space (individual step height of 17 cm).

Timing will begin on the signal to start and terminate when the subject returns with both feet to the ground level. Total time to ascend and descend steps for 1 test trial will be recorded to the nearest 100th of a second.

Use of a handrail and walking aid will be permitted if required¹. The study coordinator or designee will enter the data into the CRF.

Secondary Outcome

Patient-reported physical function (KOOS-PS).

In addition to the performance-based primary outcome measures, KOOS-PS, a self-reported measure of mobility will be included.

KOOS-Physical Function (KOOS-PS) Short Form is a parsimonious measure of physical function derived from the KOOS¹². The KOOS-Physical Function Short Form also has good internal consistency and high

test-retest reliability.

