Data regarding subject's demographic, knee radiographs, OARSI recommended physical performance measures, and KOOS subscale responses and NRS pain data will be obtained directly from subjects. All data will be coded with no information that could identify a subject. A master list with patient information and assigned study ID's will be stored in a password-protected file available only to the Principal Investigator and the Research Coordinator. Analyses will be performed on coded files. Physical files (e.g. questionnaires) will be stored in locked file cabinets in the office of the Principal Investigator.

E. Quality Assurance / Monitoring

Study staff will have proper qualifications for data entry and will receive training in data entry procedures to ensure data entered is of highest quality. Data will be entered by researchers into two separate databases developed for this study. Each database will contain the same collection points and then be reconciled to clean the data for analysis and outcome reports to the Principal Investigator. Data will be backed-up daily.

V. Data Analysis and Reporting

A. Statistical and Data Analysis:

The primary analysis will regard the change in the 3 OARSI-recommended physical performance measures between baseline and 12 weeks following injections. The three pre/post change scores will be assessed with one-sample t-test for matched pairs, using an alpha level of (.05/3) to determine statistical significant change.

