Differences between baseline and other timepoints and secondary/tertiary outcome measures will be assessed with repeated measures analyses, with time as a repeated factor to account for multiple comparisons over time. A soft-lock of the database will occur after the 6- and 12-week time points. The analyses of secondary and tertiary outcomes will involve the analyses of longitudinal data, collected at baseline, 6 weeks, 12 weeks, and 24 weeks. These response variables will be modeled using the framework of longitudinal mixed models. Each model will be based on two main effects: a random subject effect, and a fixed time effect consisting of four levels (baseline, 3 follow-up time points). The distribution of the secondary and tertiary outcome measures will be examined and transformation to a normal distribution will be performed if needed. We will use the Akaike information criterion to determine an appropriate variance/covariance structure. Each of the hypotheses of interest will be tested by examining appropriate contrasts and estimable linear forms in the overall mean and the main effects for time. Analyses will be conducted using SAS (Version 9.1.2). PROC MIXED will be used to fit the longitudinal models.

B. Outcome: We expect statistically significant and clinically meaningful improvement in physical performance, physical function, pain and quality of life 12 weeks following bilateral treatment with Zilretta.

C. Study results to subjects: The study will be registered on www.clinicaltrials.gov and results posted upon completion of the study.

D. Publication Plan: Results will be submitted for presentation at an appropriate conference and for publication in an appropriate journal for the topic of study.

VI. Bibliography / References / Literature Cited

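### The week-12 primary paired t-test drops subjects without a week-12 value and ignores their week-6 results; if loss is related to response, the single-arm estimate is biased

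*Combined protocol and SAP*

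**What the plan says.** Section V.A defines the primary analysis as the change from baseline to week 12 in the three performance measures, each tested at .05/3: "The three pre/post change scores will be assessed with one-sample t-test for matched pairs".

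The same section then turns to longitudinal methods: "Differences between baseline and other timepoints and secondary/tertiary outcome measures will be assessed with repeated measures analyses", followed by "The analyses of secondary and tertiary outcomes will involve the analyses of longitudinal data". The model described has a random subject effect and a four-level time effect, with the covariance structure chosen by AIC and fitted in PROC MIXED. The week-12 test of the performance measures is not assigned to it.

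Dropout is handled in II.C through recruitment: "To accommodate up to 14% dropout, we plan to recruit 70 subjects". Section II.D.3 adds "Subjects may discontinue the study at any time" and requires an exit form. The supplied text contains no analysis set, missing-data rule or sensitivity analysis for the primary endpoint. A short stretch, between the list of corticosteroid risks in II.F and the text on compliance reports, was not available.

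**The concern.** A subject assessed at baseline and week 6 but not at week 12 has informative data that the primary test cannot use. Recruiting 70 to keep 60 protects power, but it does not protect against bias if those who leave differ from those who stay. A controlled trial may offset some selective loss because both arms suffer it. Here there is no second arm, so any such bias passes straight into the mean change and its p-value.

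Selective loss is plausible. Subjects enter with substantial pain in both knees (II.D.1) and must avoid several other knee treatments until the end of the study (II.D.5), so those with little benefit have a reason to leave. This is inference; the documents give no evidence on who will be lost.

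The plan would also give KOOS-PS, KOOS-QoL and NRS pain a week-12 contrast that uses all visits, while the primary endpoint gets a test confined to complete pairs. It gives no reason for the difference.

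**Working it through.** **Inputs from the documents.** Effect size 0.392, alpha 0.0167, 80% power, 60 evaluable, 70 recruited, at most 14% dropout (II.C); visits at baseline and weeks 6, 12 and 24; paired t-test (V.A).

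**The plan's own figure.** With a noncentral t calculation for a paired test, 0.392 at one-sided 0.0167 needs N = 60 (power about 80%). Inflation gives 60/(1 - 0.14) = 69.8, so 70. The stated numbers reproduce, but only one-sided; two-sided, N = 71 is needed and 60 gives 71.5% power. Sidedness is a separate point.

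**Simple arithmetic.** Suppose 60 completers average 0.392 SD and the 10 lost subjects had no change. The mean over all 70 is 60 x 0.392/70 = 0.336, so the completer figure is too high by 0.056 SD.

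**Simulation assumptions (none is in the documents).** N = 70. The log-odds of loss rise by 0.5, 1 or 2 per SD of worse change, giving odds ratios e^0.5 = 1.6 to e^2 = 7.4. Visit correlations are either all 0.6, or 0.75 (baseline to follow-up) and 0.80 (week 6 to week 12). The model is an unstructured normal likelihood estimate. Bias is in SD of change.

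- Milder case: 7% lost by week 12, driven by week-6 change, half leaving before week 6. This is what 14% spread evenly over 24 weeks would give: 14% x 12/24 = 7%.
- Upper bound: all 14% lost between weeks 6 and 12, driven by week-6 change. II.C does not tie the 14% to week 12.
- Unseen-value case: loss driven by the week-12 change itself.

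Each cell gives t-test bias / model bias.

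| Case | Correlations | Slope 0.5 | Slope 1 | Slope 2 |
|---|---|---|---|---|
| Milder, 7% | 0.6 | 0.014 / 0.002 | 0.032 / 0.009 | 0.052 / 0.015 |
| Milder, 7% | 0.75, 0.80 | 0.022 / 0.009 | 0.038 / 0.014 | 0.063 / 0.024 |
| Upper bound, 14% | 0.6 | 0.034 / -0.001 | 0.063 / 0.000 | 0.094 / -0.001 |
| Upper bound, 14% | 0.75, 0.80 | 0.042 / 0.001 | 0.075 / 0.001 | 0.113 / -0.001 |
| Unseen value, 7% | 0.6 | 0.034 / 0.023 | 0.064 / 0.045 | 0.105 / 0.075 |
| Unseen value, 7% | 0.75, 0.80 | 0.036 / 0.023 | 0.066 / 0.042 | 0.105 / 0.067 |
| Unseen value, 14% | 0.6 | 0.067 / 0.046 | 0.124 / 0.088 | 0.193 / 0.141 |
| Unseen value, 14% | 0.75, 0.80 | 0.071 / 0.046 | 0.127 / 0.082 | 0.188 / 0.124 |

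**Reading the table.**
- Milder: the t-test bias is 0.014/0.392 = 4% to 0.063/0.392 = 16% of the design effect. The model removes 0.014 - 0.002 = 0.012 up to 0.063 - 0.024 = 0.039, or 3-10%. Some bias stays because those who leave before week 6 have no follow-up value to use.
- Upper bound: 0.034-0.113, or 9-29% of 0.392, with essentially none left under the model. With whole-number chair stands (assumed mean 10, SD 3) the t-test bias reaches 0.119.
- Unseen value: the share remaining under the model is 64-73% (for example 0.141/0.193 = 73%).
- Random 14% loss: no bias; SE 0.126-0.129 for the model against 0.128-0.132 for the t-test.

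**Size of the delta shift.** Shifting the missing changes by d SD moves the estimate by (fraction missing) x d. The d that cancels the bias left in the unseen-value case runs from 0.046/0.14 = 0.33 to 0.141/0.14 = 1.01 at 14% loss, and reaches 0.075/0.07 = 1.07 at 7%. The range must therefore extend somewhat beyond 1 SD.

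**The case against.** The strongest reply is that the bias is hypothetical. Nothing in the documents supports a dropout slope, and the direction could reverse if subjects who feel well stop attending. That is correct, and it is why the sizes are conditional.

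The upper bound should not carry the case: it puts the whole dropout allowance into one six-week window, although follow-up runs to week 24. In the milder case the change of method gains at most about 0.04 SD, well under one standard error. This also stands.

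The plan has retention measures: payments of $20, $20, $30 and $30 at visits 2 to 5, parking validation and encouragement around visits (III.G), and monthly reports of premature termination. Treatment is one injection per knee, so there is no repeated dosing to abandon. These may limit loss, but they do not say how missing values are analysed.

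Finally, a paired t-test matches the power calculation and is a simple choice for a pilot, and a four-level time model would yield a week-12 contrast anyway. True, but the plan does not make that contrast primary, so the stated primary result would still rest on complete pairs.

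A reader might infer that the primary estimate will be too favourable, or that a mixed model would cure the problem. The documents support neither: they are silent on who will be lost, and the model relies on data being missing at random.

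**Conclusion.** The point holds in conditional form. The named primary test excludes subjects without a week-12 value and ignores their week-6 results, and the supplied text has nothing that addresses this for the primary endpoint. Whether bias results depends on loss being related to response, which is an assumption, as are the odds ratios, visit correlations and timing.

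On those assumptions the realistic gain is modest, and only the least likely timing of loss gives a large one. The change is still worth making: it costs little, shows no precision penalty under random loss, and protects an endpoint with no control arm. It should be settled before the soft-locks after weeks 6 and 12 that V.A describes, because a later choice of method in an open-label study could look data-driven. It does not replace a sensitivity analysis for loss that depends on unseen values, where most of the bias would persist.

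**What to change.** In V.A:

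- Make the primary test for each performance measure the week-12-minus-baseline contrast at .05/3 from a PROC MIXED model with a four-level time effect, using all treated subjects with any assessment.
- Specify an unstructured covariance over the four visits through the REPEATED statement, and omit the random subject effect for these models. A random intercept adds a constant to every element of the covariance matrix; an unstructured matrix already absorbs it, so the two together are not identifiable.
- Keep the paired t-test as a supportive analysis.
- Add a delta-adjusted sensitivity analysis that shifts missing week-12 changes toward worsening, from 0 to somewhat above 1 SD of change (for example 1.25 SD, which moves the estimate by 0.14 x 1.25 = 0.175 SD at 14% loss). Set the sign for each outcome from its definition in II.E. Worsening is fewer repetitions for the chair test ("we will record the total number of chair stands (up and down equals one stand"), lower speed for the walk ("Time of one test trial will be recorded and expressed as speed (m/s) by dividing distance (40m) by total time") and longer time for the stairs ("Total time to ascend and descend steps for 1 test trial will be recorded to the nearest 100th of a second"). A wrong sign on stair time would move the estimate toward benefit.

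The cost is a few lines of text and a little more analysis, with a procedure the plan already names. The limit is that the model corrects bias only if data are missing at random and a post-baseline value exists.
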